9.3 Analysis Sets

For the purposes of analysis, the following analysis sets are defined:

Participant Analysis Set	Description
Randomized	All participants that have a randomization number
Safety Analysis Set (SafAS)	Participants who have received the study vaccine(s). All participants will have their safety analyzed according to the vaccine they actually received and study intervention group. Safety data recorded for a vaccine received out of the protocol design will be excluded from the analysis (and listed separately).
Immunogenicity analysis set (IAS)	Subset of randomized participants who received at least 1 dose of study vaccine. Participants will be analyzed according to the vaccine they actually received and study intervention group.

9.4 Statistical Analyses

The statistical analysis plan (SAP) will be finalized prior to database lock and it will include a more technical and detailed description of the statistical analyses described in this section. This section is a summary of the planned statistical analyses of the most important endpoints including primary and key secondary endpoints.

9.4.1 General Considerations

All statistical analyses will be performed under the responsibility of the Sponsor's Biostatistics Platform using the SAS® software, Version 9.4 or above (SAS Institute, Cary, North Carolina, USA).

For the derivation of immunogenicity endpoints, all values strictly under the lower limit of quantification (LLOQ) will be treated as LLOQ/2, and all values above or equal to the upper limit of quantification (ULOQ) will be treated as ULOQ.

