2) To describe the immune response elicited by Moderna COVID-19 Vaccine administered concomitantly or singly, in each study intervention group.	Endpoints for Immunogenicity Objective #2 
 Individual anti-S binding IgG concentration on D01 and 21 days after injection of Moderna COVID-19 Vaccine (D22) Individual anti-S binding IgG concentration ratio D22/D01 2-fold-rise and 4-fold-rise in anti-S binding IgG concentration 21 days post-injection D01

4 Study Design

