5.1 Inclusion Criteria

Participants are eligible for the study only if all of the following criteria are met:

Age

I01: Aged ≥ 65 years of age on the day of inclusion^a.

Type of participant and disease characteristics

^a “ ≥ 65 years” means from the day of the 65th birthday onwards.

- I02: In good health or with underlying medical condition(s) that are judged to be stable by the Investigator. A stable medical condition is defined as disease not requiring significant change in therapy or hospitalization for worsening disease during the 3 months before enrollment.
- I03: Participants who previously received 2 injections of Moderna COVID-19 Vaccine with the second dose received at least 5 months before V01^a.

Informed Consent

- I04: Informed consent form has been signed and dated.

Other Inclusions

- I05: Able to attend all scheduled visits and to comply with all study procedures.

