9.4.3 Other Analysis

The ratios of post-vaccination GMTs between concomitant and single injections will be presented for the five antigens with 2-sided 95% CIs.

Subgroup analyses will also be performed as complementary analyses; in particular, immunogenicity will be described according to serostatus at baseline, previous influenza vaccination, and age, as appropriate according to number of subjects in the respective subgroups.

Other analyses will be described in the SAP.

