3.4.3 Immunogenicity Endpoints

The IAS will be used. Immunogenicity endpoints will be summarized with 95% CI by actual study group and vaccine received, for each timepoint. Cumulative distribution frequencies will also be provided to support that concomitant vaccine administration does not interfere with the assay readout, particularly at the extremes of high and low titer results.

In addition, the ratios of post-vaccination GMTs between concomitant and single injections will be presented for the five antigens with 2-sided 95% CIs. A baseline adjustment will be applied using an ANCOVA model of the D22 log10 titer/concentration with vaccine group and D01 log10 titer as factor and covariate, respectively.

Subgroup analyses will also be performed as complementary analyses; in particular, immunogenicity will be described according to serostatus at baseline (pre-vaccination < or >= to LLOQ), previous influenza vaccination, gender and age group, as appropriate according to number of participants in the respective subgroups.

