4.2.3.2 Fold-rise

For the HAI and SARS COV-2 immune response, the derived endpoint fold-rise is driven by both baseline (D01) and post-baseline (D22) computed values as described in Section 4.2.3.1 and is computed as individual ratio:

- 21 days after vaccination divided by D01.

For the SARS COV-2 immune response:

- If the computed fold-increase is ≥ 2 , the derived ≥ 2 -fold rises indicator will be “Yes”, otherwise ≥ 2 -fold rises will be “No”.
- If the computed fold-increase is ≥ 4 , the derived ≥ 4 -fold rises indicator will be “Yes”, otherwise ≥ 4 -fold rises will be “No”.

Note: if pre-vaccination (D01) or post-vaccination (D22) values is missing, the fold-rise is missing.

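### Anti-S results at or above the ULOQ are analysed as exact values; if about a quarter or more of D22 values get there, the Group 1 vs Group 3 ratio can be biased, with too narrow a CI

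*Protocol*

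**What the plan says.** Protocol 9.4.1 states that "all values above or equal to the upper limit of quantification (ULOQ) will be treated as ULOQ", and SAP 4.2.3.1 repeats the rule. SAP 3.4.4.2 only refers back to it.

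Two analyses use the capped values:

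- **Between-arm ratio.** Protocol 9.4.3: "The ratios of post-vaccination GMTs between concomitant and single injections will be presented for the five antigens with 2-sided 95% CIs". SAP 3.4.3 obtains it "using an ANCOVA model of the D22 log10 titer/concentration with vaccine group and D01 log10 titer as factor and covariate".
- **Fold-rise.** SAP 4.2.3.2 says that it "is driven by both baseline (D01) and post-baseline (D22) computed values as described in Section 4.2.3.1". The Protocol Table 3.1 endpoint is "2-fold-rise and 4-fold-rise in anti-S binding IgG concentration 21 days post-injection D01".

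For HAI, Protocol 8.1.2.1 gives a top reportable titer (10240 or above). For the anti-S ELISA, Protocol 8.1.2.2 gives neither a ULOQ nor a rule for sera above it. No count of values at the ULOQ and no censored-data analysis is planned.

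**The concern.** A result at or above the ULOQ is known only to be at least that large. Entering it as exact removes part of the upper tail. If one arm responds more strongly, more of its tail is removed, so the difference between arms shrinks; the residual variance shrinks too, so the CI narrows around a shifted estimate.

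D22 anti-S IgG is where this could happen. Inclusion criterion I03 admits "Participants who previously received 2 injections of Moderna COVID-19 Vaccine with the second dose received at least 5 months before V01", and Groups 1 and 3 then receive a third dose.

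The ratio is the only between-arm immunogenicity estimate that the plan names. With no margin or test, a reader has only the estimate and its CI to judge interference by.

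**Working it through.** **Inputs from the documents.** Evaluable participants per group (Protocol 9.2): 100 × (1 − 0.05) = 95, which reproduces the plan's figure. Model: log10 D22 on group and log10 D01.

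**Assumed, because the documents give none of these.** Log10 SD 0.40 in both arms (range 0.3 to 0.5); D01–D22 correlation 0.5; true Group 1/Group 3 ratio 1.0, 0.80 or 0.67; 0, 10, 25 or 50% of Group 3 at the ULOQ on D22; true geometric mean rise of 5, 10 or 20.

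**1. Precision without a ceiling.** SE = 0.40 × √(1 − 0.5²) × √(2/95) = 0.0503. With t(187) = 1.973 the half-width is 0.0992 on log10, that is ×/÷ 1.256.

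**2. Closed form for the bias.** With a = (c − μ)/σ, the mean of a normal variable capped at c is μΦ(a) − σφ(a) + c(1 − Φ(a)). Take a 25% ceiling, c = 0.6745 × 0.40 = 0.2698:

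- Group 3, μ = 0: −0.40 × 0.3178 + 0.2698 × 0.25 = −0.0597.
- Group 1, μ = log10(0.67) = −0.1739, a = 1.109: the mean is −0.2009.
- Difference −0.1412, so the estimated ratio is 10^(−0.1412) = 0.722 against a true 0.67.

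**3. Simulation of the planned ANCOVA** (SD 0.40, 95 per arm, 1500 replicates per cell). Each cell gives the estimate, the fold half-width and the coverage of the 95% CI.

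| Group 3 at ULOQ | True 0.67 | True 0.80 | True 1.0 |
|---|---|---|---|
| 0% | 0.671, 1.258, 0.953 | 0.803, 1.257, 0.949 | 0.998, 1.257, 0.948 |
| 10% | 0.687, 1.240, 0.943 | 0.815, 1.239, 0.938 | 0.996, 1.234, 0.941 |
| 25% | 0.725, 1.215, 0.889 | 0.836, 1.210, 0.929 | 1.000, 1.203, 0.951 |
| 50% | 0.789, 1.168, 0.467 | 0.885, 1.160, 0.727 | 1.001, 1.149, 0.945 |

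SDs of 0.3 and 0.5 give nearly the same estimates. At a 25% ceiling coverage is then 0.839 and 0.904 (true 0.67), and 0.909 and 0.932 (true 0.80). At 50% it is 0.282 and 0.554, and 0.593 and 0.793.

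**4. Unequal spread.** With a true ratio of 1, SD 0.5 in Group 1 and 0.3 in Group 3, the formula in step 2 gives 0.89 at a 10% ceiling and 0.85 at 25%. The estimate moves away from 1.

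**5. Right-censored normal regression, same terms** (SD 0.40, 300 replicates per cell). True 0.67: 0.669 at 25% and 0.668 at 50%, half-widths 1.254 and 1.267, coverage 0.923 at both. True 0.80: 0.794 and 0.810, half-widths 1.249 and 1.269, coverage 0.943 at both. The Monte Carlo error of a coverage near 0.95 is √(0.95 × 0.05/300) = 0.013, so 0.923 is about two standard errors low.

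**6. Fold-rise.** The largest ratio that can be computed is ULOQ/D01, so D01 above ULOQ/4 (or ULOQ/2) rules out a 4-fold (or 2-fold) 'Yes'. The true rise is undetermined only if D22 is also at or above the ULOQ. With bivariate normal log10 values (SD 0.40, correlation 0.5), the percentages of an arm for the 4-fold rise, at 10/25/50% ceilings, are:

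| True rise | D01 above ULOQ/4 | Of these, D22 also at ULOQ (undetermined) |
|---|---|---|
| 5 | 6.4 / 18.0 / 40.4 | 2.3 / 9.4 / 28.3 |
| 10 | 1.1 / 4.8 / 16.0 | 0.6 / 3.1 / 12.8 |
| 20 | 0.1 / 0.8 / 4.0 | 0.1 / 0.6 / 3.6 |

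At a 25% ceiling the 4-fold rate falls from 59.5% to 54.2% (rise 5), 84.0% to 81.7% (rise 10) and 96.0% to 95.5% (rise 20).

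**The case against.** **The ceiling may never be reached.** This stands. Silence about re-testing in Protocol 8.1.2.2 does not show that out-of-range sera are left unresolved. With no value at the ULOQ nothing changes, and the striking coverage figures need half of Group 3 to be there.

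**The plan already looks at the extremes.** SAP 3.4.1 and 3.4.3 provide quartiles, maxima and cumulative distribution displays. A pile-up would be visible, but the ratio, its CI and the responder rates would stay uncorrected.

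**The study is descriptive.** True, so no decision rule is broken. The harm is to interpretation.

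**A censored model has limits.** It relies on log-normality in a tail that cannot be observed, although SAP 3.4.1 already assumes log10 normality. It leaves any D01 value at the ULOQ capped as a covariate. It does not transfer simply to HAI, where the titer is the geometric mean of two runs capped separately. These are reasons to set it beside the ANCOVA for anti-S only, not to replace the ANCOVA.

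**Stronger readings that a reader might infer, and that are not supported:**

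- That capping always favours a finding of no interference. Step 4 shows the opposite can occur.
- That the CI always under-covers. At a true ratio of 1 with equal spread it narrows but coverage stays near 0.95.
- That every participant with D01 above ULOQ/4 is misclassified. If D22 is below the ULOQ, 'No' is correct.
- That fold-rise rates are understated in every arm. Only arms with D22 values at the ceiling are affected, and Group 2 receives no COVID-19 vaccine.

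**Conclusion.** The concern holds conditionally. If about 25% or more of D22 anti-S values reach the ULOQ, the Group 1 vs Group 3 ratio is biased and its CI under-covers whenever the true ratio differs from 1 or the spreads differ. With similar spread the bias is toward 1: at a 25% ceiling a true 0.67 reads about 0.72 with coverage near 0.89. At 10% or less with similar spread the error is about 0.02 and coverage about 0.94, which is negligible.

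The fold-rise loss is smaller: at a 25% ceiling, 0.6% to 9.4% of a boosted arm is undetermined for the 4-fold rise, depending on the true rise.

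All sizes rest on the assumed SD, correlation, true ratio and rise, and ceiling share. Nothing in the documents says which row of the tables will apply.

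**What to change.** - **SAP 4.2.3.1 and 3.4.3:** report the number and percentage at or above the ULOQ by arm and visit. If any D22 anti-S value is affected, report beside the planned ANCOVA a right-censored normal regression on log10 concentration with the same group and D01 terms.
- **SAP 4.2.3.2:** when D22 is at or above the ULOQ and ULOQ/D01 is below the threshold, flag the indicator as undetermined. Report the 2-fold and 4-fold rates twice, with these counted as all 'No' and as all 'Yes'. Do not exclude them, because being undetermined is itself related to a high response. No change is needed where ULOQ/D01 already meets the threshold; the present rule scores that 'Yes'.

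The cost is SAP wording, one count table and one standard model. The added model depends on upper-tail log-normality and gives a slightly wider CI (×/÷ 1.254 against 1.215 at a 25% ceiling, true ratio 0.67). If no value reaches the ULOQ, the planned results are unchanged.

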9.4.2 Study Endpoints

All analyses will be descriptive. No hypotheses are planned to be tested.

For the main parameters, 95% CIs for the point estimates will be calculated using the normal approximation after log transformation for quantitative data (GMCs and GM of individual ratios) and exact binomial distribution (Clopper-Pearson method, quoted by Newcombe) for single proportions.

For immunogenicity analyses the IAS will be used. Results will be presented by actual study group and vaccine received for each timepoint. For the analysis of SARS COV-2 immune response, the serological results will be received in ELU/mL but will be expressed in BAU/mL for the analysis. The following formula will be used for converting the concentration units from ELU/mL to BAU/mL:

$$\text{Result (BAU/mL)} = \text{Result (ELU/mL)} / 7.9815$$

For safety analyses the SafAS will be used. Results will be presented by actual study group and vaccine received.

9.4.3 Other Analysis

The ratios of post-vaccination GMTs between concomitant and single injections will be presented for the five antigens with 2-sided 95% CIs.

Subgroup analyses will also be performed as complementary analyses; in particular, immunogenicity will be described according to serostatus at baseline, previous influenza vaccination, and age, as appropriate according to number of subjects in the respective subgroups.

Other analyses will be described in the SAP.

9.5 Interim Analyses

The statistical analysis will be performed in two or three steps, depending on the availability of immunogenicity data: the safety objectives up to D22 will be analyzed first and the immunogenicity objectives will be analyzed in a second step, after immunogenicity data have been released. No impact is expected on immunogenicity results as the conduct of immunogenicity assays will remain blinded. At last, the final analysis will be performed when safety data up to D181 is released.

10 Supporting Documentation and Operational Considerations

10.1 Appendix: Regulatory, Ethical, and Study Oversight Considerations

Note: The term “participant” is used throughout this protocol. However, the term “subject” will be used in the CRF in order to comply with the Clinical Data Interchange Standards Consortium (CDISC) requirements. Similarly, “legally acceptable representative” is used in the protocol whereas “guardian” is used in the CRF.

10.1.1 Regulatory and Ethical Considerations

- This study will be conducted in accordance with the protocol and with the following:
 - Consensus ethical principles derived from international guidelines including the Declaration of Helsinki and Council for International Organizations of Medical Sciences (CIOMS) International Ethical Guidelines
 - Applicable ICH Good Clinical Practice (GCP) Guidelines
 - Applicable laws and regulations (eg, data protection law as General Data Protection Regulation [GDPR])
- The protocol, informed consent form (ICF), product-related information (ie, US PI for Fluzone High-Dose Quadrivalent vaccine and the Investigator’s Brochure for Moderna COVID-19 Vaccine), and other relevant documents (eg, advertisements) must be submitted to an IRB/IEC by the investigator or the Sponsor (according to local regulations) and reviewed and approved by the IRB/IEC before the study is initiated
- Any amendments to the protocol will require IRB/IEC approval before implementation of changes made to the study design, except for changes necessary to eliminate an immediate hazard to study participants
- Protocols and any substantial amendments to the protocol will require health authority approval prior to initiation except for changes necessary to eliminate an immediate hazard to study participants.
- The investigator will be responsible for the following:
 - Providing written summaries of the status of the study to the IRB/IEC annually or more frequently in accordance with the requirements, policies, and procedures established by the IRB/IEC
 - Determining whether an incidental finding (as per Sanofi policy) should be returned to a participant and, if it meets the appropriate criteria, to ensure the finding is returned (an incidental finding is a previously undiagnosed medical condition that is discovered unintentionally and is unrelated to the aims of the study for which the tests are being performed). The following should be considered when determining the return of an incidental finding:

- The return of such information to the study participant (and/or his/her designated healthcare professional, if so designated by the participant) is consistent with all applicable national, state, or regional laws and regulations in the country where the study is being conducted, and
- The finding reveals a substantial risk of a serious health condition or has reproductive importance, AND has analytical validity, AND has clinical validity.
- The participant in a clinical study has the right to opt out of being notified by the Investigator of such incidental findings. In the event that the participant has opted out of being notified and the finding has consequences for other individuals, eg, the finding relates to a communicable disease, Investigators should seek independent ethical advice before determining next steps.
- In case the participant has decided to opt out, the Investigator must record in the site medical files that she/he does not want to know about such findings.
- Notifying the IRB/IEC of SAEs or other significant safety findings as required by IRB/IEC procedures
- Providing oversight of the conduct of the study at the site and adherence to requirements of 21 CFR, ICH guidelines, the IRB/IEC, European regulation 536/2014 for clinical studies (if applicable), European Medical Device Regulation 2017/745 for clinical device research (if applicable), and all other applicable local regulations

As applicable, according to Directive 2001/20/EC, the Sponsor will be responsible for obtaining approval from the Competent Authorities of the EU Member States and/or Ethics Committees, as appropriate, for any amendments to the clinical trial that are deemed as “substantial” (ie, changes which are likely to have a significant impact on the safety or physical or mental integrity of the clinical trial participants or on the scientific value of the trial) prior to their implementation.

10.1.2 Financial Disclosure

Information related to financial disclosure is described in the Investigator's contract.

10.1.3 Informed Consent Process

- The investigator or his/her representative will explain the nature of the study to the participant and answer all questions regarding the study.
- Participants must be informed that their participation is voluntary. Participants will be required to sign a statement of informed consent that meets the requirements of 21 CFR 50, local regulations, ICH guidelines, Health Insurance Portability and Accountability Act (HIPAA) requirements, where applicable, and the IRB/IEC or study center.
- The medical record must include a statement that written informed consent was obtained before the participant was enrolled in the study and the date the written consent was obtained. The authorized person obtaining the informed consent must also sign the ICF.

- The actual ICF used at each center may differ, depending on local regulations and IEC / IRB requirements. However, all versions must contain the standard information found in the sample ICF provided by the Sponsor. Any change to the content of the ICF must be approved by the Sponsor and the IEC / IRB prior to the form being used.
- If new information becomes available that may be relevant to the participant's willingness to continue participation in the study, this will be communicated to him / her in a timely manner. Such information will be provided via a revised ICF or an addendum to the original ICF.
- Participants must be re-consented to the most current version of the ICF(s) during their participation in the study.
- A copy of the ICF(s) must be provided to the participant.

The ICF will contain a specific section that addresses the use of remaining mandatory samples for optional exploratory research, unless prohibited by local laws or IRBs/IECs. The investigator or designee will explain to each participant the objectives of the exploratory research. Participants will be told that they are free to refuse to participate and may withdraw their consent at any time and for any reason during the storage period.

Recruitment Procedures

Before the start of the study, the Investigator or sub-investigator will contact an appropriate pool of potential participants and invite them to participate in the study. The site will ensure that any advertisements used to recruit participants (eg, letters, pamphlets, posters) are submitted to Sanofi Pasteur for review prior to submission to the IEC/IRB for approval.

10.1.4 Data Protection

All personal data collected and/or processed in relation to this study will be handled in compliance with all applicable Privacy & Data Protection laws and regulations, including the GDPR (General Data Protection Regulation). The study Sponsor is the Sanofi company responsible for ensuring compliance with this matter, when processing data from any individual who may be included in the Sanofi databases, including Investigators, nurses, experts, service providers, Ethics Committee members, etc.

When archiving or processing personal data pertaining to the Investigator and/or to the participants, the Sponsor shall take all appropriate measures to safeguard and prevent access to this data by any unauthorized third party.

Protection of participant data

Data collected must be adequate, relevant and not excessive, in relation to the purposes for which they are collected. Each category of data must be properly justified and in line with the study objective.

- Participants race and ethnicity will be collected in this study because these data are required by the FDA (27).

- Participants will be assigned a unique identifier by the Sponsor. Any participant records or datasets that are transferred to the Sponsor or its service providers will be identifiable only by the unique identifier; participant names or any information which would make the participant identifiable will not be transferred to the Sponsor.
- The participant must be informed that his/her personal study-related data will be used by the Sponsor in accordance with applicable data protection law. The level of disclosure must also be explained to the participant as described in the informed consent.
- The participant must be informed that his/her medical records may be examined by Clinical Quality Assurance auditors or other authorized personnel appointed by the Sponsor, by appropriate IRB/IEC members, and by inspectors from regulatory authorities.
- Participants must be informed that their study-related data will be used for the whole “drug development program”, ie, for this trial as well as for the following steps necessary for the development of the investigational product, including to support negotiations with payers and publication of results.

Protection of data related to professionals involved in the study

- Personal data (eg, contact details, affiliation(s) details, job title and related professional information, role in the study, professional resume, training records) are necessary to allow Sanofi to manage involvement in the study and/or the related contractual or pre-contractual relationship. They may be communicated to any company of the Sanofi group (“Sanofi”) or to Sanofi service providers, where needed.
- Personal data can be processed for other studies and projects.
- In case of refusal to the processing of personal data by or on behalf of Sanofi, it will be impossible to involve the professionals in any Sanofi study. In case the professionals have already been involved in a Sanofi study, they will not be able to object to the processing of their personal data as long as they are required to be processed by applicable regulations. The same rule applies in case the professionals are listed on a regulatory agencies disqualification list.
- Personal data can be communicated to the following recipients:
 - Personnel within Sanofi or partners or service providers involved in the study
 - Judicial, administrative and regulatory authorities, in order to comply with legal or regulatory requirements and/or to respond to specific requests or orders in the framework of judicial or administrative procedures. Contact details and identity may also be published on public websites in the interest of scientific research transparency
- Personal data may be transferred towards entities located outside the Economic European Area, in countries where the legislation does not necessarily offer the same level of data protection or in countries not recognized by the European Commission as offering an adequate level of protection. Those transfers are safeguarded by Sanofi in accordance with the requirement of European law including, notably:
 - The standard contractual clauses of the European Commission for transfers towards our partners and service providers,

- Sanofi's Binding Corporate Rules for intra-group transfers.
- Professionals have the possibility to lodge a complaint with Sanofi leading Supervisory Authority, the "Commission Nationale de l'Informatique et des Libertés" (CNIL) or with any competent local regulatory authority.
- Personal data of professionals will be retained by Sanofi for up to thirty (30) years, unless further retention is required by applicable regulations.
- In order to facilitate the maintenance of Investigators personal data, especially if they contribute to studies sponsored by several pharmaceuticals companies, Sanofi participates in the Shared Investigator Platform (SIP) and in the Transcelerate Investigator Registry (IR) project (<https://transceleratebiopharmainc.com/initiatives/investigator-registry/>). Therefore, personal data will be securely shared by Sanofi with other pharmaceutical company members of the Transcelerate project. This sharing allows Investigators to keep their data up-to-date once for all across pharmaceutical companies participating in the project, with the right to object to the transfer of the data to the Transcelerate project.
- Professionals have the right to object to the processing, to request for access to and the rectification of their personal data, as well as their erasure (where applicable) by contacting the Sanofi Data Protection Officer: Sanofi DPO - [name] (to contact Sanofi by email, visit <https://www.sanofi.com/en/our-responsibility/sanofi-global-privacy-policy/contact>).

